7.7 Storage and analysis of samples

Blood sampling will be undertaken by a trained phlebotomist in accordance with Northumbria-Healthcare Foundation Trust Policy.

The samples will be transported in UN 3373 packaging to the University of Newcastle Upon Tyne. Approximately 10mls of blood will be drawn from the subject during their routine blood monitoring clinic.

If a subject does not have good venous access and refuses more than one attempt at blood draw, this participant will be withdrawn from the study.

The Sponsor will provide the collection bottles.

The samples will be tested at the University of Newcastle Upon Tyne.

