3.3 Outcome measures

3.3.1 Primary endpoint/outcome

The primary outcome measure is the responses to the Methotrexate Adherence and the Rheumatoid Arthritis Knowledge questionnaires. Subjects will be randomised 50:50 to receive the Rheumatoid Arthritis information booklet. Those participants who do not receive the booklet at randomisation will receive it 3 – 6 months later when the participant returns for their routine Methotrexate blood monitoring appointment. The aim of this is to determine whether the intervention of the Rheumatoid

Arthritis information booklet has an impact on patient Methotrexate management. All patients will be given the Methotrexate Adherence questionnaire and the RA Questionnaire at screening and again 3 – 6 months later.

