3.3.2 Secondary endpoints/outcomes

The secondary outcome measure is the measurement of RC-MTX polyglutamate levels in a venous blood sample at two timepoints from all study patients to detect if Methotrexate Adherence correlates with RC-MTX polyglutamate levels.

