4 TRIAL DESIGN

A parallel group design where each group of participants receives only one of the study treatments. The participants will be randomised to one of two groups of 50 participants each. One group will receive the Rheumatoid Arthritis information booklet at screening and both groups will have blood taken for RC-MTX polyglutamate levels at screening and 3 – 6 months later, the group who did not receive the booklet will receive the Rheumatoid Arthritis information booklet when they return 3 – 6 months later. Following a peer review of the protocol, participants who have to stop taking Methotrexate due to eg infection or abnormal blood laboratory result, will be able to continue in the study provided they have been on their original stable dose of MTX for at least 4 weeks prior to taking the second blood tests.

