8.2 Statistical analysis plan

Sample size estimation

This is a pilot study, and as such key outcomes of interest relate to recruitment rates, drop outs a/loss to follow up and data quality and missing data for completion of the adherence questionnaire. We will also collect data on change in adherence with medication and change in polyglutamate levels in red blood cells from baseline to follow-up in each group. This will help inform a sample size calculation for a fully powered clinical trial. For an external pilot study designed to establish the sample size for a definitive randomised controlled trial, with a normally distributed continuous primary clinical outcome, Teare, et al¹ recommend a minimum sample size in each group of 35. To allow for a maximum drop-out rate of 30% at follow-up, we aim to recruit 50 subjects per group (100 in total).

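### Section 7.7 withdraws a participant from the whole study when a secondary blood sample cannot be obtained, although the primary questionnaires need no blood

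*Protocol*

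**What the plan says.** **The rule.** Protocol section 7.7 deals with a participant who does not have good venous access and adds that one who "refuses more than one attempt at blood draw, this participant will be withdrawn from the study". Both conditions must be met: poor access, and refusal of more than one attempt. The consequence is withdrawal from the study, not only from blood sampling.

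**The outcomes.** Section 3.3.1 states: "The primary outcome measure is the responses to the Methotrexate Adherence and the Rheumatoid Arthritis Knowledge questionnaires". All participants are to be "given the Methotrexate Adherence questionnaire and the RA Questionnaire at screening and again 3 – 6 months later". Section 3.3.2 places the blood sample second: "The secondary outcome measure is the measurement of RC-MTX polyglutamate levels in a venous blood sample at two timepoints from all study patients". Section 4 gives it the same timing: "both groups will have blood taken for RC-MTX polyglutamate levels at screening and 3 – 6 months later".

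**The withdrawal list.** Section 7.6 names withdrawal of consent, stopping or changing methotrexate, inability to return to clinic, and the investigator's opinion of the participant's best interests. A failed or refused blood draw is not on it.

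**The pilot's purpose and size.** On what the pilot is to measure, ending with how fully one of the two questionnaires is answered, section 8.2 reads: "key outcomes of interest relate to recruitment rates, drop outs a/loss to follow up and data quality and missing data for completion of the adherence". It sets a minimum of 35 per group and recruits 50 per group: "To allow for a maximum drop-out rate of 30% at follow-up".

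**The concern.** A missing secondary measurement ends the collection of primary data. No section lets such a participant continue with the questionnaires alone, and none says how data from withdrawn participants are handled.

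Two things are at stake. The first is avoidable loss of follow-up questionnaires. The second is the meaning of the drop-out rate. Drop-out is one of the quantities that this pilot exists to estimate for a definitive trial, and the rule adds to it people who might willingly have completed the questionnaires. The number reported would partly describe the rule and not the participants.

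Sections 7.6 and 7.7 also give staff different answers. Under 7.6 alone the participant stays; under 7.7 the participant leaves.

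**Working it through.** **1. The plan's own figure.** Inputs from section 8.2: 35 per group as a minimum, 30% maximum drop-out. 35 / (1 − 0.30) = 50 per group, 100 in total. This reproduces the stated target. Conversely, 50 × 0.70 = 35, so at the maximum drop-out there is no slack.

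**2. Where the rule costs primary data.** The questionnaires and the blood draws fall at the same two time points (sections 3.3.1 and 4). There are three cases:

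- *Screening draw fails after randomisation.* The participant is withdrawn and the follow-up questionnaires are never collected. This loss is clear.
- *Screening draw fails before randomisation.* This acts as a screen failure, and since section 8.1 recruits until 100 are reached, the person might be replaced. Appendix 4 marks the laboratory test, eligibility assessment and randomisation all at screening, with no order given.
- *Follow-up draw fails.* The follow-up questionnaires may already be complete. The order within the visit is not fixed. The loss of primary data may be nil, although the participant could still be counted as a drop-out.

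**3. Size.** The protocol gives no rate of poor access with refusal, so the rate f per draw is an assumption. Taking only the clear case, with every failed screening draw falling after randomisation:

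- f = 2%: 100 × 0.02 = 2 participants
- f = 5%: 100 × 0.05 = 5 participants
- f = 8%: 100 × 0.08 = 8 participants

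**4. Effect on the sample size.** If these participants fall within the 30%, at least 35 per group remain and the target of 50 stands. If they come on top of a true 30% drop-out:

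- f = 2%: 50 × 0.70 × 0.98 = 34.3 per group
- f = 5%: 50 × 0.70 × 0.95 = 33.25 per group
- f = 8%: 50 × 0.70 × 0.92 = 32.2 per group

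**5. Effect on the estimated drop-out.** With true attrition a, the observed rate is f + (1 − f) × a. With a = 30%, the plan's maximum:

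- f = 2%: 0.02 + 0.98 × 0.30 = 31.4%
- f = 8%: 0.08 + 0.92 × 0.30 = 35.6%

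The pilot would then report 31.4% to 35.6% where attrition from all other causes is 30%, unless the causes are separated.

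**The case against.** **The trigger is narrow.** A failed draw alone does not lead to withdrawal. Participants are established methotrexate patients at routine blood monitoring, and the study sample is taken when routine blood is drawn (section 5, Appendix 1). The true rate may be low. This stands, and it is why no rate is claimed.

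**The sample matters to the study.** The title names methotrexate levels, section 3.3.2 wants samples from all study patients, and section 8.2 uses the change in polyglutamates to inform the later trial. Wanting paired samples is reasonable. But withdrawing the participant does not produce the missing sample; it only adds missing questionnaires.

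**Sampling-related loss is itself feasibility information.** That is true, and a reason to count it under its own name and not inside drop-out.

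A reader might infer more than the text supports:

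- *That data already collected are discarded.* The protocol does not say so. It is silent on data from withdrawn participants.
- *That about 10 of 100 are lost, a third of the 30-participant allowance.* This comes from 1 − 0.95² = 9.8%. It needs an unanchored 5% rate, independence of the two draws, and every failure at either draw costing primary data. Step 2 of the working shows that the last condition is not established.
- *That the loss is informative because refusal reflects attitudes to treatment.* This is possible, but nothing in the protocol shows it, and nothing makes the rule act differently in the two groups.

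**Conclusion.** The point holds in a limited form. As written, section 7.7 ends a participant's time in the study over a secondary sample, while the primary outcome could still be collected; section 7.6 does not support it. The existence of the rule and its conflict with the order of the outcomes are certain from the text.

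The size is not. About 2 to 8 of 100 participants rests on an assumed 2% to 8% failure-and-refusal rate at screening, with the failure falling after randomisation. It would be smaller if some failures come before randomisation. The sample size is correctly derived, and it stays adequate if these withdrawals fall within the 30% allowance. The more durable harm is to the pilot's drop-out estimate, which would mix two different causes at any non-zero rate. The rule should be changed because the change is cheap, not because the loss is shown to be large.

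**What to change.** - **Section 7.7:** replace the withdrawal sentence. Where a sample cannot be obtained, the polyglutamate result for that visit is recorded as missing, and the participant, if willing, stays in the study and completes the questionnaires. The right in section 7.2 to withdraw at any time is unchanged.
- **Section 7.6:** make it agree with the amended 7.7, so that staff have one answer.
- **Analysis:** analyse polyglutamates on the available samples, and count missing samples separately from drop-out.

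The cost is one amended sentence and a matching check of section 7.6. No visit, procedure or needle attempt is added, and the target of 50 per group stays. The downside is that a smaller share of the retained participants will have a complete pair of samples.

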7.8 End of trial

The sponsor will notify the REC within 90 days of completion of the study.

8 STATISTICS AND DATA ANALYSIS

8.1 Planned recruitment rate

It is expected that the project should run for 18 months from the date of R&D approval being given. It is estimated that 10 – 15 patients per month will be recruited, until a total of 100 patients have been recruited into the study.

8.2 Statistical analysis plan

Sample size estimation

This is a pilot study, and as such key outcomes of interest relate to recruitment rates, drop outs a/loss to follow up and data quality and missing data for completion of the adherence questionnaire. We will also collect data on change in adherence with medication and change in polyglutamate levels in red blood cells from baseline to follow-up in each group. This will help inform a sample size calculation for a fully powered clinical trial. For an external pilot study designed to establish the sample size for a definitive randomised controlled trial, with a normally distributed continuous primary clinical outcome, Teare, et al¹ recommend a minimum sample size in each group of 35. To allow for a maximum drop-out rate of 30% at follow-up, we aim to recruit 50 subjects per group (100 in total).

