Adherence to Methotrexate in Rheumatoid Arthritis: Effect of an Information Booklet on Methotrexate Levels

Methotrexate Adherence Project

Methotrexate Adherence Project

RESEARCH REFERENCE NUMBERS

PROTOCOL VERSION NUMBER 2 20th August 2018

Sponsor: Northumbria Healthcare NHS Foundation Trust

IRAS Number: 189766

CPMS 37811

TRIAL SUMMARY

Trial Title	Adherence to Methotrexate in Rheumatoid Arthritis: Effect of an Information Booklet on Methotrexate Levels	
Internal ref. no. (or short title)	Methotrexate Adherence Project	
Clinical Phase	IV	
Trial Design	Mixed Methods	
Trial Participants	Subjects with Rheumatoid Arthritis on a stable dose of Methotrexate	
Planned Sample Size	100 participants	
Treatment duration	3 – 6 months	
Follow up duration	none	
Planned Trial Period	18 months	
	Objectives	Outcome Measures
Primary	Does Education using an Information Booklet have an impact on Methotrexate Adherence and Disease Management	The responses of 100 patients with RA on Methotrexate to the Methotrexate Adherence Questionnaire and the Rheumatoid Arthritis Knowledge Questionnaire will be analysed qualitatively and quantitatively
Secondary	Do changes in Methotrexate Polyglutamate Assays detect Methotrexate Adherence	Methotrexate Polyglutamate Assays will be measured in venous blood samples of the study population

FUNDING AND SUPPORT IN KIND

FUNDER(S)	FINANCIAL AND NON FINANCIAL SUPPORT GIVEN
Chugai Pharmaceuticals Ltd UK	Financial support given
University of Newcastle Upon Tyne	Processing of blood samples
Northumbria Healthcare NHS Foundation Trust	Study Sponsor

[figure not shown]
KEY TRIAL CONTACTS

Chief Investigator	
[name]
 
Senior Research Nurse
 
Northumbria Healthcare NHS Foundation Trust
 
Co-Investigator:
 
[name]
 
Consultant Rheumatologist
 
Northumbria Healthcare NHS Foundation Trust

Trial Co-ordinator	
[name]
 
Senior Research Nurse
 
[contact]
 
[name]

Sponsor	
Northumbria Healthcare NHS Foundation Trust
 
North Tyneside General Hospital
 
Clinical Trials Office, [name]
 
[name]

Joint-sponsor(s)/co-sponsor(s)	N/A
Funder(s)	Chugai Pharmaceuticals Ltd UK
Clinical Trials Unit	N/A
Key Protocol Contributors	[name]
Statistician	N/A
Trials pharmacist	N/A
Committees	The INFLAME patient group, North Tyneside

LIST of CONTENTS

GENERAL INFORMATION	Page No.
TITLE PAGE	1
RESEARCH REFERENCE NUMBERS	2
TRIAL SUMMARY	3

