3 OBJECTIVES AND OUTCOME MEASURES/ENDPOINTS

3.1 Primary objective

The primary objective of this project is to determine if a Rheumatoid Arthritis information booklet increases understanding of Rheumatoid Arthritis in patients with this disease and leads to better disease management through drug adherence.

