8.3 Primary outcome analysis

Data analysis will be supported by standard statistical software (e.g. SPSS, SAS) and supervised by a statistician. Given the pilot nature of the study, and the stated outcomes of interest, much of the analysis will be of a descriptive nature using standard summary outcomes (e.g. frequency, mean, median, range, standard deviation). Where appropriate (e.g. assessment of effect size) for clinical outcomes of interest, inferential analysis will be conducted using standard tests depending on the distribution and nature of the data (e.g. t-test, Mann-Whitney U test, Wilcoxon signed ranks test, Chi-squared test). Significance will be set at 5% and two tailed tests used as appropriate.

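### The Trial Summary and Section 3 set out to determine whether the booklet works, but Section 8.2 sizes a pilot with feasibility outcomes that Section 3 never lists

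*Protocol*

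**What the plan says.** **Effect of the booklet as the primary question.** The Trial Summary gives the primary objective as "Does Education using an Information Booklet have an impact on Methotrexate Adherence and Disease Management". Section 3.1 gives it as to "determine if a Rheumatoid Arthritis information booklet increases understanding of Rheumatoid Arthritis in patients with this disease and leads to better disease management". Section 3.3.1 says: "The primary outcome measure is the responses to the Methotrexate Adherence and the Rheumatoid Arthritis Knowledge questionnaires". It adds that the purpose of the 50:50 randomisation is to find out whether the booklet affects how patients manage methotrexate. Section 2 also names the two questionnaires as the primary outcome measures.

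**Feasibility as the primary question.** Section 8.2 calls the study a pilot and says that its "key outcomes of interest relate to recruitment rates, drop outs a/loss to follow up and data quality and missing data" for the adherence questionnaire. Adherence appears there as an addition: "We will also collect data on change in adherence with medication and change in polyglutamate levels in red blood cells". These data are to inform a later, fully powered trial. Section 8.2 does not mention the knowledge questionnaire. The sample size is 35 per group, taken from a published recommendation for external pilots and raised to 50 for drop-out of at most 30%.

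**Analysis.** Section 8.3, headed as the primary outcome analysis, appeals to the pilot nature of the study and plans mostly descriptive summaries. For clinical outcomes it allows inferential tests where appropriate, and it closes: "Significance will be set at 5% and two tailed tests used as appropriate".

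**The concern.** A trial is judged against its stated primary objective and outcome. Here the section that fixes them and the section that justifies the sample size describe different studies. Someone who reads Section 3 expects an answer on whether the booklet works. Someone who reads 8.2 expects recruitment, retention and completeness figures, and finds that Section 3 does not list them as outcomes at all.

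The practical risk is a non-significant comparison. Set against 3.1, it invites the conclusion that the booklet has no effect, although the sample was never chosen to support that conclusion. The feasibility results, which the sample was chosen for, have no place among the declared outcomes and could be under-reported.

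A separate statistical analysis plan cannot settle this, because the protocol itself fixes the objective, the primary outcome and the purpose of the sample size.

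**Working it through.** **1. The two readings side by side**

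| Item | Trial Summary, Sections 2 and 3 | Sections 8.2 and 8.3 |
|---|---|---|
| Purpose | Whether the booklet has an impact | External pilot to inform a later powered trial |
| Main outcomes | Adherence and knowledge questionnaires | Recruitment, drop-out, data quality, missing data |
| Adherence | Primary | Additional data |
| Knowledge | Primary | Not mentioned in 8.2 |
| Feasibility outcomes | None listed | Key |
| Analysis | – | Mainly descriptive, with 5% tests where appropriate |

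**2. The plan's own figure**

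Inputs from 8.2: 35 per group, 30% drop-out. 35 / (1 − 0.30) = 50 per group, 100 in total. The stated target is reproduced exactly. The arithmetic is right and serves the pilot purpose.

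**3. What that sample offers the Section 3 objective**

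The protocol states no effect size, SD or power for either questionnaire, so standardised differences of 0.3 and 0.5 SD are assumed here. Other inputs: 1:1 allocation (3.3.1), two-sided 5% (8.3), and a two-sample t-test on follow-up scores without baseline adjustment.

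For n evaluable per arm and standardised difference d:
- degrees of freedom = 2n − 2, and the noncentrality parameter = d × √(n/2). Power is the probability that the noncentral t exceeds the critical value in absolute size.
- 95% CI half-width in SD units = t(0.975, 2n − 2) × √(2/n).

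For n = 35: half-width = 1.995 × √(2/35) = 1.995 × 0.239 = 0.477.
For n = 50: half-width = 1.984 × √(2/50) = 1.984 × 0.200 = 0.397.

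| Evaluable per arm | Power at 0.3 SD | Power at 0.5 SD | Difference for 80% power | 95% CI half-width |
|---|---|---|---|---|
| 35 (maximum drop-out) | 24% | 54% | 0.68 SD | 0.48 SD |
| 50 (no drop-out) | 32% | 70% | 0.57 SD | 0.40 SD |

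**4. What a null result would mean**

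If the observed difference were exactly zero with 35 per arm, the interval would run from about −0.48 to +0.48 SD. With 50 per arm it would run from about −0.40 to +0.40 SD. Either interval leaves open no effect and a moderate benefit, so neither answers the question in 3.1.

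**5. Effect of baseline adjustment**

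Both questionnaires are also taken at screening (3.3.1). With an assumed baseline-to-follow-up correlation of 0.5, the residual variance is multiplied by 1 − 0.5² = 0.75. At 35 per arm the half-width falls to about 0.41 SD, and power at 0.5 SD rises to about 66%.

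**The case against.** The protocol is not uniformly confirmatory. Sections 1 and 2 speak of exploring an effect, the Trial Summary gives the design as mixed methods with qualitative as well as quantitative analysis, and 8.3 acknowledges the pilot and is largely descriptive. On this view the defect is inconsistent labelling rather than an efficacy trial given a pilot's sample. That is a fair description, and it narrows the point. It does not remove it, because 3.1 and 3.3.1, which define the objective and the outcome, both speak of determining an effect.

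The power figures can also be called pessimistic: 30% is a maximum drop-out, and baseline scores are available. Both are true, and the figures for 50 per arm and for adjustment are given for that reason.

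Four stronger readings are tempting, but the documents do not support them:
- **That the trial cannot deliver its primary answer.** A large effect would probably be detected: 80% power is reached at about 0.68 SD with 35 per arm and 0.57 SD with 50.
- **That the definitive trial will be sized on the effect observed here.** Section 8.2 says only that the data will help inform that calculation. The mention of effect size in 8.3 is an example of when testing may be used and sets no sizing rule.
- **That the figure of 35 is a rule for estimating an SD only.** Section 8.2 describes it as a recommendation for pilots that establish the sample size of a definitive trial. The title of the cited paper refers to design parameters in general.
- **That two primary questionnaires raise the false-positive rate to 1 − 0.95² = 9.75%.** That needs independent outcomes and a rule that success on either one suffices. The protocol states no such rule.

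**Conclusion.** The contradiction stands on the protocol's own text. The Trial Summary, 3.1 and 3.3.1 set a question about the booklet's effect, with two questionnaires as the primary outcome. Section 8.2 sets feasibility outcomes that Section 3 does not list, and leaves out one of the two questionnaires. Section 8.3 follows the pilot but keeps 5% tests.

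The sample size is correctly calculated for the pilot. It is not justified for the stated objective, and a null result could not answer that objective. The size of the gap rests on the assumed effects of 0.3 and 0.5 SD, on a continuous score and on no baseline adjustment. Full retention or baseline adjustment would narrow the gap somewhat without closing it at these effects.

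This should be corrected, because it decides what the trial may conclude.

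**What to change.** Align the Trial Summary, Section 2, 3.1 and 3.3.1 with 8.2:
- Make the primary outcomes recruitment, retention and questionnaire completeness, together with the parameters needed to size the definitive trial, such as the SDs of the questionnaire scores.
- Make the between-arm differences in adherence and knowledge secondary. Report them as estimates with 95% confidence intervals, and amend 8.3 so that a 5% test does not serve as a verdict on whether the booklet works.
- Mention the knowledge questionnaire in 8.2.

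If the sponsor prefers to keep the efficacy objective, it should name one primary questionnaire score and state the effect that the planned N can detect, with the SD and power assumed.

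The cost is a wording change and, on the first route, a more modest stated claim. No extra patients are needed.
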